3.7.3. Post-surgery

Patients were intensively treated in the intensive care unit (ICU), intermediate room, and standard room according to clinical conditions. The researcher observed and recorded the amount of bleeding accumulated until chest tube removal and blood products transfusion units of blood components during treatment. Transfusion will be given when there is an indication for transfusion. The indication for *packed red cell* (PRC) transfusion was Hb <10 g/dL, with a target of Hb >10 g/dL. The indication for platelet transfusion was platelets <100,000 U/ μ L, with a target of platelets >100. The indication for fresh frozen plasma (FFP) transfusion is if APTT > 1.5 times the control, the transfusion target is activated partial thromboplastin clotting time (APTT) < 1.5 times the control. Cryoprecipitate was given if fibrinogen < 100 mg/dL, and the transfusion target was fibrinogen > 100 mg. Observation of bleeding was recorded from initial

bleeding, 6 hours, 24 hours, and 48 hours, or until chest tube removal if the bleeding was <200 mL/24 hours.

Bleeding management protocols were performed if there was excessive or massive bleeding post-surgery. A single researcher conducted all observations to maintain data reliability which was then recorded for further processing.

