3.7.1. Exclusion criteria

1. Patients who expressed unwillingness to become research subjects.
2. Patients who have an allergy to tranexamic acid.
3. Patients were undergoing urgent/emergency surgery and minimally invasive surgery
4. The patient underwent a double procedure of simultaneous aortic and mitral valve surgery.
5. Patients with a history of bleeding disorders (coagulopathy) such as clotting factor deficiency and heparin-induced thrombocytopenia or use of intravenous anticoagulants other than heparin at the time of surgery.
6. Patients with a history of thromboembolic disease.
7. Patients with active Infective endocarditis
8. Patients with a history of previous cardiac surgery
9. Patients with a estimated glomerular filtration rate <30 mL/min or on dialysis
10. Patients who receiving oral therapy with clopidogrel, aspirin, dabigatran, or rivaroxaban in the last five days
11. Patients who receiving chronic warfarin therapy who have not stopped their medication and have an international normalized ratio (INR) >1.5 before surgery
12. Patients with pre-operative thrombocytopenia (<50,000 platelets per μ L)
13. Pregnancy or breast feeding patients
14. Patients who refusal of blood products
15. Patients with a pericarditis

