3.10. Operational Definition

Table 3.2 Operational definitions-

| Variables | Definition | Measurement | Variable Scale | Variable Value |
|--|--|---|----------------|--|
| Administration of topical tranexamic acid | Intrapericardial administration of 5 g tranexamic acid in 50 mL 0.9% NaCl after protamine administration and before sternotomy closure in cardiac surgery | - | Nominal | 
 • Treatment (tranexamic acid) • Control (NaCl 0.9%) |
| Amount of bleeding | | | | |
| Initial bleeding | Amount of blood accumulated in the patient's water-sealed drainage (WSD) system shortly after cardiac surgery | Observation of the volume of blood collected in the WSD system | Numerical | mL |
| 6-hour bleeding | Amount of blood accumulated in the water-sealed drainage (WSD) system of a patient 6-hour post cardiac surgery | Observation of the volume of blood collected in the WSD system | Numerical | mL |
| 24-hour bleeding | Amount of blood accumulated in the water-sealed drainage (WSD) system of a patient 24 hour-post cardiac surgery | Observation of the volume of blood collected in the WSD system | Numerical | mL |
| 48-hour bleeding | Amount of blood accumulated in the water-sealed drainage (WSD) system of a patient 48 hours- post cardiac surgery | Observation of the volume of blood collected in the WSD system | Numerical | mL |
| Blood Transfusion Requirements | | | | |
| Packed red cell (PRC) transfusion | Amount of PRC transfusions received in post cardiac surgery patients with Hb levels <10 g/dL to reach Hb levels >10 g/dL before discharge. | Observation of the volume of PRC received by the patient | Numerical | mL |
| Platelet transfusion ⁴⁹ | Amount of blood platelet transfusions received in post cardiac surgery patients with platelets <100,000 U/ μ L to reach levels of 100,000 U/ μ L or in platelet dysfunction. | Observation of the volume of Platelet transfusion received by the patient | Numerical | mL |
| Fresh Frozen plasma (FFP)Transfusion ⁴⁹ | Amount of blood FFP transfusions received by post cardiac surgery patients with international normalized ratio (INR) >1.5 to reach 1.5 | Observation of the volume of FFP received by the patient | Numerical | mL |

| Variables | Definition | Measurement | Variable Scale | Variable Value |
|---|---|--|----------------|---|

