3.12. Data processing flow

The data of the research subjects collected using the forms were verified and compiled using SPSS software for Microsoft Windows version 20.0 in the form of descriptive tables. Data normality and statistical analysis for each variable were performed using the same software. The tests used to analyze the two dependent variables (amount of bleeding and blood products transfusion after cardiac surgery) were the independent T-test (for normal data distribution) and the Mann-Whitney test (for abnormal data distribution).

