1.4 Detailed cost plan

| | |
|--|------------------------|
| Proposal drafting (printing and photocopying costs) | Rp600.000,00 |
| Submission of ethics and research permits | Rp900.000,00 |
| Data collection (observation, consumables) | Rp15.000.000,00 |
| Preparation of research report (printing and photocopying costs) | Rp1.500.000,00 |
| Journal publication | Rp5.000.000,00 |
| Total | Rp23.000.000,00 |

1.5 *Dummy table*

Tabel Error! No text of specified style in document..1 Sample table of experimental and control group characteristics

| Variables | Experimental Group | Control Group (Placebo) | P-value |
|---------------------------------------|--------------------|-------------------------|---------|
| Age (years) | Rerata ± SD | Rerata ± SD | |
| Gender | | | |
| Male | n (%) | n (%) | |
| Women | n (%) | n (%) | |
| Body surface area (m ²) | Mean ± SD | Mean ± SD | |
| Comorbidities | | | |
| Hypertension | n (%) | n (%) | |
| Diabetes mellitus | n (%) | n (%) | |
| Preoperative hemoglobin | Mean ± SD | Mean ± SD | |
| Preoperative hematocrit | Mean ± SD | Mean ± SD | |
| Preoperative APTT | Mean ± SD | Mean ± SD | |
| Preoperative INR | Mean ± SD | Mean ± SD | |
| Preoperative creatinine | Mean ± SD | Mean ± SD | |
| Postoperative hemoglobin | Mean ± SD | Mean ± SD | |
| Duration of aortic cross clamp | Mean ± SD | Mean ± SD | |
| Duration of use of heart-lung machine | Mean ± SD | Mean ± SD | |

Tabel Error! No text of specified style in document..2 Sample output table of CABG results in experimental and control groups

| Primary outcome output | Control group (n=22) | Experimental group with TXA (n = 22) | P-value |
|----------------------------------|----------------------|--------------------------------------|---------|
| Volume of chest drain bleeding | | | |
| Initial bleeding (mL) | Mean ± SD | Mean ± SD | |
| 6-hour bleeding (mL) | Mean ± SD | Mean ± SD | |
| 24-hour bleeding (mL) | Mean ± SD | Mean ± SD | |
| 48-hour bleeding (mL) | Mean ± SD | Mean ± SD | |
| Blood Transfusion | | | |
| PRC transfusion (mL) | Mean ± SD | Mean ± SD | |
| FFP transfusion (mL) | Mean ± SD | Mean ± SD | |
| TC transfusion (mL) | Mean ± SD | Mean ± SD | |
| Cryoprecipitate transfusion (mL) | Mean ± SD | Mean ± SD | |

Table Error! No text of specified style in document..3 Sample output table of OPCAB results in experimental and control groups

| Primary outcome output | Control group (n=22) | Experimental group with TXA (n = 22) | P-value |

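### PRC and platelet transfusion volumes depend partly on preoperative haemoglobin and platelet count, but the planned comparisons adjust for neither

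*Combined protocol and SAP*

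**What the plan says.** Section 3.7.3 (Post-surgery) links each blood product to a fixed laboratory value. The indication for PRC "transfusion was Hb <10 g/dL, with a target of Hb >10 g/dL". For platelets, "The indication for platelet transfusion was platelets <100,000 U" per µL. Table 3.2 (section 3.10) turns the rule into the outcome, recorded in mL: "Amount of PRC transfusions received in post cardiac surgery patients with Hb levels <10 g/dL to reach Hb levels >10 g/dL before discharge". The platelet entry has the same form and also allows transfusion for platelet dysfunction. Neither outcome is a change from baseline.

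The inclusion criteria (3.5.1) and exclusion criteria (3.7.1) set no haemoglobin limit. The only platelet limit is exclusion 12: "Patients with pre-operative thrombocytopenia (<50,000 platelets per" µL).

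Section 3.12 says the tests for bleeding and transfusion "were the independent T-test (for normal data distribution) and the Mann-Whitney test (for abnormal data distribution"). It names no covariate. "Preoperative hemoglobin" is a row in the sample table of group characteristics (1.5 Dummy table), as are preoperative APTT and INR. None of the three is among the confounders in Table 3.1, and 3.12 adjusts for none of the confounders that are listed there.

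Transfusion is not a side endpoint. It is the subject of hypotheses 4 to 6, it has its own sample-size calculation in 5.6, and all three sample results tables place it under the primary outcome heading.

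**The concern.** With a fixed trigger and a fixed target, the volume a patient receives depends on where that patient starts as well as on how much is lost. A patient may enter already below the PRC trigger, or with a platelet count between 50,000 and 100,000. Variation in starting values then adds to the variation in the outcome, and a chance difference in starting values between arms carries over into the transfusion comparison.

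The plan tests each surgery group separately with 22 per arm, so such differences are not rare. The baseline table would show one, with a P-value, but would not correct for it. A transfusion difference could be partly produced or partly hidden by preoperative haemoglobin, a variable the trial already intends to tabulate.

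**Working it through.** **1. Entry limits against transfusion triggers**

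| Product | Trigger | Entry limit | Can enter past the trigger? |
|---|---|---|---|
| PRC | Hb <10 g/dL (3.7.3, Table 3.2) | none | yes |
| Platelets | <100,000 (3.7.3, Table 3.2) | excluded if <50,000 | yes, from 50,000 to just under 100,000 |
| Fresh frozen plasma (FFP) | APTT >1.5 × control (3.7.3) or INR >1.5 (Table 3.2) | warfarin not stopped with INR >1.5; history of coagulopathy | unclear until the two definitions are reconciled |

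**2. The plan's own figure.** Section 5.6 uses z-values 1.96 and 0.842, SD 1.072 units and a difference of 1 unit:

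n = 2[(1.96 + 0.842) × 1.072 / 1]² = 18.04 per arm, as stated. Bleeding gives 20.05, so 20 governs; adding 10% gives 22 per arm, and 22 × 2 × 3 = 132. The steps below use this SD in units, because the plan gives no SD in mL, the scale on which transfusion is recorded.

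**3. Chance imbalance.** With 22 per arm, a standardised baseline difference has SE = √(2/22) = 0.302 (normal approximation; no stratification on haemoglobin is described).

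- One surgery group: P(|difference| >0.5 SD) = 2[1 − Φ(0.5/0.302)] = 9.7%.
- At least one of three: 1 − (1 − 0.097)³ = 26.4%.
- With 20 evaluable per arm: 11.4% and 30.4%.

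**4. Effect of a 0.5 SD imbalance on the unadjusted result.** Let r be the correlation between preoperative haemoglobin and PRC transfusion. It is an assumption; the documents give no value. With 20 per arm:

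- Shift in the difference = r × 0.5 × 1.072 units.
- SE = 1.072 × √(2/20) = 0.339. Given the imbalance, and with no treatment effect, the difference has mean equal to the shift and SD 0.339 × √(1 − r²). The conditional type I error is the chance that it falls outside ±1.96 × 0.339.

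**5. Gain from adjustment.** Residual variance is multiplied by 1 − r², which is equivalent to multiplying the sample size by 1/(1 − r²). Power is for 1 unit with 20 per arm and SD 1.072 × √(1 − r²); unadjusted power is 83.9%.

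| Assumed r | Shift (units) | Type I error given a 0.5 SD imbalance | Variance removed | Sample-size factor | Adjusted power |
|---|---|---|---|---|---|
| 0.3 | 0.16 | 6.5% | 9% | 1.10 | 87.1% |
| 0.4 | 0.21 | 7.6% | 16% | 1.19 | 89.6% |
| 0.5 | 0.27 | 8.9% | 25% | 1.33 | 92.6% |
| 0.6 | 0.32 | 10.3% | 36% | 1.56 | 95.8% |

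These figures assume a linear relation and ignore the degree of freedom spent on the covariate.

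**The case against.** **The size is not in the documents.** Neither r nor the share of patients entering past a trigger is stated. Unadjusted power for the plan's own transfusion assumption is already 83.9% with 20 per arm, so no more patients are needed. This stands, and it limits the point to a gain in precision.

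**A plain linear model may fit badly.** Volumes are zero for untransfused patients and likely to be skewed, which is why the plan keeps the Mann-Whitney test in reserve. A trigger-and-target rule also gives a threshold relation, so the gains in the table may not be reached in full. This stands as a limit on the numbers and changes the form of the model, but it does not justify leaving the covariate out.

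**It is part of a wider gap.** Table 3.1 lists confounders and 3.12 uses none. True, but preoperative haemoglobin is not even on that list, and the transfusion rule itself makes it a natural covariate for PRC volume.

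**FFP does not support the same claim.** A reader might infer from exclusion 11, "Patients who receiving chronic warfarin therapy who have not stopped their medication and have an international normalized ratio (INR) >1.5 before surgery", that someone who stopped warfarin but still has a raised INR enters already meeting the FFP criterion. That rests on a strict reading of loosely worded text. Exclusion 5 removes patients with a history of coagulopathy, and Table 3.3 has warfarin stopped 4-5 days before surgery. The criterion itself is also unsettled: section 3.7.3 says FFP "transfusion is if APTT > 1.5 times the control", while Table 3.2 uses INR. The objection holds here until those passages are reconciled.

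**Platelet count may well be recorded.** It is absent from the dummy table, but that is a sample table, section 3.8 says the form holds preoperative examination results, and exclusion 12 cannot be applied without a count. The documents do not show that it goes uncollected.

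**Conclusion.** The point holds for PRC and platelet volumes, as a shortfall in precision and robustness. Entry leaves the starting values open, the outcomes depend on them through fixed triggers and targets, and the planned tests ignore them. The chance of a haemoglobin imbalance above 0.5 SD is about 10% in one surgery group and 26% in at least one of three. For assumed r of 0.3 to 0.6, adjustment removes 9% to 36% of residual variance and raises power from 83.9% to between 87.1% and 95.8%.

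Two stronger readings are tempting and not supported:

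- **That the treatment comparison is biased.** Patients are randomised, so baseline status does not favour either arm on average and the overall type I error stays nominal. The raised error rates in the table apply only once an imbalance of that size has occurred.
- **That a patient past the trigger at entry reaches the outcome whatever the study fluid does.** The outcome is a volume in mL, given until a target is reached. A patient who starts below the trigger and bleeds less can need less blood, so such patients can carry treatment effect. Nothing in the documents says they would be transfused alike in both arms, and an analysis leaving them out could discard informative patients from arms of about 22.

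This should be changed because it is nearly free. It does not invalidate the design.

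**What to change.** Amend section 3.12 before the arms are compared:

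1. Compare PRC volume within each surgery group by a model with treatment and preoperative haemoglobin as terms. Report the adjusted difference with a confidence interval. If volumes are skewed or have many zeros, use robust or bootstrap standard errors, or a rank-based ANCOVA, and state the choice in advance.
2. Do the same for platelet volume with the preoperative platelet count, and show that count in the baseline table.
3. For FFP, first reconcile the APTT indication in 3.7.3 with the INR definition in Table 3.2. Then adjust for the matching preoperative value; both are already in the dummy table.
4. Report, by arm and surgery group, how many patients met each product's trigger before surgery. Keep them in the analysis.

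Transfusion triggers and eligibility are left as they are. The cost is a few sentences in 3.12, at most one more laboratory value copied from the record, and one or two degrees of freedom per model.

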3.7.2. Perioperative

Patients who became research subjects underwent coronary artery bypass surgery according to standard operating procedures at RSPJNHK. After inducing anesthesia, undergoing sternotomy, and installing a heart-lung bypass machine (*on-pump*), the patient underwent the primary procedure. Then the research protocol was carried out with either treatment or control (placebo) after the heart-lung bypass machine stopped and before the sternum was closed by previously clamping the chest tube. After skin closure was completed, the chest tube clamps were reopened, and internal suction was performed, followed by connecting the chest tube with a *water-sealed drainage* system to accommodate post-surgical intrathoracic bleeding. The sternal closure to skin suturing process is done within 30-45 minutes.

In OPCAB group, after the graft anastomosis with OPCAB technique was completed, before sternal closure, the patient was given an intervention in

the form of topical tranexamic acid (5g/50mL) or placebo (50mL normal saline) dissolved in 100mL normal warm saline (37° C) which was inserted into the pericardial cavity including mediastinal tissue and allowed to stand for five minutes. It was then cleaned and sternal closure was performed.

The study subjects then underwent heart valve surgery according to the standard operating procedures of RSJPDHK, which began with induction of anesthesia, sternotomy, and CPB insertion. After the heart-lung bypass machine stopped, the chest tube was installed and clamped, the Subject then received one of the placebo or treatment fluids which were divided into two administrations, 50 mL of the first liquid was given to the intrapericardium and 50 mL of the second liquid was given to the sternum. The sternum was closed to the skin with an estimated completion of 30-45 minutes. Chest tube clamps were opened and connected to a water-sealed drainage (WSD) system to remove residual bleeding in the thorax after surgery.

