3.13. Research flow

[figure not shown]

Table 3.3 Research protocol

| TIME | LOCATION | ACTION |
|-------------|-----------------|---|
| D-1 | Preoperative | 
1. Patient's informed consent, signature on a consent form2. Put a green research sticker on the patient's status3. Ensure STOP ACE inhibitors (Captopril, Ramipril, Lisinopril) and ARBs (Candesartan, Valsartan) 24 hours preoperatively.4. Make sure to STOP antiplatelet drugs 3-7 days preoperatively5. Make sure to STOP Warfarin 4-5 days preoperatively6. Ensure Heparin STOP 4-6 hours preoperatively7. Ensure STOP LMWH 12-48 hours preoperatively8. Record all required patient data on the questionnaire |
| D+0 | Operating Room | 
1. Induction, intubation2. Standard operating procedures3. The surgeon administers topical tranexamic acid (5 g in 50 mL NS) or placebo in 100 mL, 50 mL after protamine administration, and 50 mL before closing the sternum.4. Chest tube clamps should not be opened until the skin closure process is complete. |
| D+0 | ICU | 
1. Calculate the initial bleeding when the patient arrives at the intensive care unit2. Collect blood coagulation examination data (blood, hematocrit, PT/APTT, INR)3. Count the amount of bleeding from the chest tube in the first 6 hours and 24 hours4. Disconnect the chest tube if the amount of bleeding is <200 mL in 24 hours |
| D+1 | ICU | 
1. Count the amount of bleeding from the chest tube in the second 24 hours (if the chest tube is still in place)2. Chest tube removal when the amount of bleeding is <200 mL in the second 24 hours |

| TIME | LOCATION | ACTION |
|--------------------------|----------------|---|
| | | 3. Calculate the use of blood component transfusion (PRC, FFP, TC, Cryoprecipitate) |
| D+2 – hospital discharge | ICU - Wardroom | 1. Record clinical output results according to the questionnaire (total amount of drain production and transfusion use of blood components) |

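### Initial bleeding is read at ICU arrival, an unfixed and unrecorded time after drainage starts, and the later readings have no consistently stated time zero, so the first primary-outcome row loses precision

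*Combined protocol and SAP*

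**What the plan says.** - **Start of drainage.** Section 3.7.2, on-pump coronary surgery: "After skin closure was completed, the chest tube clamps were reopened, and internal suction was performed". The valve paragraph has the same order of events. The OPCAB paragraph does not mention clamping. Table 3.3 does, in an operating-room row that applies to all patients.
- **First reading.** Table 3.2 defines it as "Amount of blood accumulated in the patient's water-sealed drainage (WSD) system shortly after cardiac surgery", with no clock time. Table 3.3 (D+0, ICU) says: "Calculate the initial bleeding when the patient arrives at the intensive care unit".
- **Later readings.** Table 3.2 dates the volumes from surgery: "system of a patient 6-hour post cardiac surgery" and "system of a patient 24 hour-post cardiac surgery", and likewise at 48 hours. Table 3.3, in the ICU row, says: "Count the amount of bleeding from the chest tube in the first 6 hours and 24 hours", with no start point. Section 3.7.3 opens its list with "Observation of bleeding was recorded from initial" bleeding and continues with 6-, 24- and 48-hour observations, also without a start point.
- **Use.** Initial bleeding in mL is the first row under the primary-outcome heading in all three results tables of section 1.5. Section 3.12 compares the groups by t-test or Mann-Whitney test, and neither takes account of observation time. Section 3.8 lists the amount of bleeding among the form's contents but no reading times.

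**The concern.** A drained volume can be compared between patients only if the collection time is the same or is known. Here the first volume runs from unclamping to arrival in intensive care, so a patient transferred slowly shows more initial bleeding than one transferred quickly at the same drain rate. That variation adds to the outcome variance of a test with 22 patients per arm.

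The early readings matter most for this drug. The topical-application study described in section 6.3.3 reports a larger reduction in the first 3 hours (36%) than over 24 hours (25%). For the later readings, staff following Table 3.2 and staff following Table 3.3 could reasonably start the clock at different moments, because only one of the two tables states when it starts.

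**Working it through.** **1. The plan's own figure.** Section 5.6 uses SD 339.021 mL, difference 300 mL, z-values 1.96 and 0.842:

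n = 2 × [(1.96 + 0.842) × 339.021 / 300]² = 20.05 per group.

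The plan takes 20 and adds 10% to reach 22. By the normal approximation, power is 79.9% at 20 and 83.5% at 22 per group. The calculation names no time point, so it does not size the initial-bleeding comparison.

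**2. Initial bleeding: model and assumptions.** The documents give neither transfer times nor drain rates. Assume:
- the interval T from unclamping to ICU arrival is uniform over 15 to 60 minutes: mean 37.5, SD 45/√12 = 12.99 minutes;
- the drain rate R is independent of T, with a between-patient CV of 50%;
- the volume is R × (T + p), where p is the number of minutes of drainage pooled behind the clamp and released on opening.

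Then CV²(volume) = (1 + CV²(R)) × (1 + CV²(T + p)) − 1. With a fixed reading time it is 0.25.

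| Pooled drainage p | CV²(T + p) | CV²(volume) | Variance ratio | Equivalent n per arm (22 / ratio) |
|---|---|---|---|---|
| 0 min | (12.99/37.5)² = 0.120 | 1.25 × 1.120 − 1 = 0.400 | 1.60 | 13.75 |
| 30 min | (12.99/67.5)² = 0.037 | 1.25 × 1.037 − 1 = 0.296 | 1.19 | 18.6 |
| 45 min | (12.99/82.5)² = 0.025 | 1.25 × 1.025 − 1 = 0.281 | 1.12 | 19.6 |

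The 30 and 45 minutes are the closure time in section 3.7.2. That pooling continues at the patient's own later drain rate is a further assumption.

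**3. The same in power.** Simulation: gamma-distributed rates, 22 per arm, a 36% lower rate on treatment (the 3-hour effect in section 6.3.3, borrowed as an assumption), Welch test, 20,000 runs.
- Rate CV 50%: power is about 81% with a fixed time. With a variable time it is about 61% with no pooling and about 74% to 76% with 30 to 45 minutes pooled.
- Rate CV 100%, no pooling: about 27% against 22%. The row is then weak either way, and timing adds little.

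**4. Later readings.** Add timing noise to the planning SD: SD = √[339.021² + (drain rate × timing SD)²]. Using 339.021 mL for a late reading is an assumption.

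| Assumed drain rate and timing SD | Added SD (mL) | Total SD (mL) | Power at 20 per group |
|---|---|---|---|
| none | 0 | 339.0 | 79.9% |
| 50 mL/h, 0.5 h | 25 | 339.9 | 79.7% |
| 100 mL/h, 0.5 h | 50 | 342.7 | 79.1% |
| 200 mL/h, 1 h | 200 | 393.6 | 67.4% |

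Only fast drainage combined with wide timing variation costs much, and that combination is unlikely at 24 hours.

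**5. Table 3.2 against Table 3.3.** Table 3.2 has a stated origin (surgery) and Table 3.3 has none. At 48 hours they also differ in what is counted: Table 3.2 has blood accumulated to 48 hours, while Table 3.3 counts the second 24-hour period only.

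**The case against.** Four objections deserve weight.

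- **Two conflicting clocks.** A reader might infer that Tables 3.2 and 3.3 start the 6- and 24-hour clocks at different points, the second at ICU arrival. The documents do not say so. The ICU row shows where the count is made, and its wording is compatible with a clock starting at surgery. What can be shown is a missing time zero. A 15 to 60 minute difference would be 4% to 17% of 6 hours (15/360 and 60/360), but that compares two possible definitions. It is not variation between patients under one definition, so it is not a loss of precision.
- **Whether the initial volume is included.** Table 3.2 describes each volume as accumulated in the drainage system, which largely answers this for the 6- and 24-hour values.
- **Size.** A reader might take the fall from 81% to 61%, or from 22 to about 14 per arm, as the expected loss. It assumes that nothing has pooled at unclamping, although section 3.7.2 keeps the tubes clamped through a 30 to 45 minute closure. It is therefore an upper-end case for these inputs, for one of four time points. For OPCAB, pooling is less certain, because clamping appears only in the general row of Table 3.3.
- **Bias.** One researcher makes all observations, and allocation is randomised and blinded. With blinding intact, timing noise is balanced in expectation. A single observer improves consistency of reading but does not control when the patient arrives.

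The core stands: following the plan exactly gives first volumes over unequal, unrecorded intervals.

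**Conclusion.** The point holds for initial bleeding. Its reading time depends on transfer, is not recorded, and is ignored by the planned test. Under the assumed 15 to 60 minute interval and 50% rate CV, its variance is about 1.1 to 1.2 times that of a fixed-time reading if blood pooled during closure is released at unclamping, and up to 1.6 times if it is not. These inputs are assumptions, and the true loss could be smaller or larger.

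For the 6-, 24- and 48-hour readings the defect is an inconsistently stated time zero. Its effect on the 24-hour volume is probably negligible: about 0.2 points of power at 50 mL/h with a timing SD of 0.5 h. The documents give no 6-hour SD, so the effect there cannot be sized separately. The consequence is lost precision and comparability. Nothing here shows bias between the arms. The change should be made because it is cheap.

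**What to change.** In section 3.7.3 and Tables 3.2 and 3.3:

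1. Set one time zero for all bleeding readings: opening of the chest-tube clamps, or connection of the drain if the tubes were not clamped.
2. Record the clock time of time zero and the actual clock time of every reading.
3. Take the first reading at a fixed time after time zero (for example 1 hour) instead of at ICU arrival. Recording the arrival time alone would help, but the volumes would still cover unequal intervals.
4. Define the 6- and 24-hour volumes as cumulative from time zero, including the initial volume, and state whether the 48-hour value is cumulative or covers the second 24 hours only.

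The cost is protocol wording, extra time fields on the form and one scheduled reading. It needs no added patients, visits or staff and leaves the sample size unchanged. The small downside is that the first volume must be read at a set time.
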